## 15.0 Risks to Subjects\*

- 15.1 Confidentiality and privacy: A risk of this research is a loss of privacy or confidentiality. To minimize this risk and protect the participant's identity, we will store health information coded, using a subject ID # instead of the participant's name. Coding and locking of data will minimize the risk of confidentiality loss. All data collected during visits linking study and health information will also be coded and stored in the PI's laboratory. Only the PI and limited research personnel will have access to the key to the code that links coded data with the identity of the participant (which will be password protected) and this key will be stored in the PI's locked office (Rm 308A).
- 15.2 Questionnaires: Participants may feel uncomfortable providing any personal information to questions. Subject will be advised to skip any questions they do not wish to answer.
- 15.3 Cardiovascular function: There are no known risks associated with the process of measuring endothelial function or arterial stiffness. Subjects may however feel uncomfortable when the blood pressure cuffs are inflated.
- 15.4 Lung/Respiratory Muscle Function and Inspiratory Muscle Training: There is risk of dizziness, coughing, and/or feeling short of breath during the tests.
- 15.5 Functional Status: Participants may experience muscle tightness, muscle soreness and fatigue, shortness of breath, and lightheadedness. A research staff member will stand an arm's length away while you are performing the balancing portion of the test for precautionary measures.

## 16.0 Potential Benefits to Subjects\*

- 16.1 Individual subjects who take part in this research may or may not experience improvements in pulmonary and/or physical functions. Information acquired during this study will contribute to the literature that seeks to determine the efficacy of this form of training.

- Encryption: All electronic data collected during the study will be encrypted to ensure its security during transmission and storage. Data will be transmitted securely using encrypted methods and stored on secure hard drives.
- Physical Controls: All physical documents and materials containing patient data will be stored in locked cabinets or rooms with access restricted to authorized personnel only.
- Separation of Identifiers and Data: Identifiers, such as names and, will be stored separately from study data to ensure the privacy and confidentiality of participants. Identifiers will only be used to link study data to the participants, and they will be removed once the data analysis is complete.

**PROTOCOL TITLE: Effects of high-intensity inspiratory muscle training as a pre-cardiac rehabilitation intervention on cardiovascular functions in patients with heart disease**

**17.3** The data will be handled study-wide as follows: All written data collection forms and electronic data will be handled and stored by principal investigator. The written data collection forms will be stored in PI's locked office in a locked filing cabinet. The research electronic data will be stored using the UIC Health Box Data Folder electronic database.

Authorized research personnel will maintain a master sheet which has the subject's name linked to their code. This sheet will be maintained within the UIC Health Box Data Folder designated for the study. All personal identifiable data will be destroyed 10 years after study completion. Results published will not include names of subjects. Some personal health information will be collected during the screening process, including name, contact information, and for individuals who meet the inclusion and exclusion criteria, dates of birth and CABG.

**18.0 Provisions to Monitor the Data to Ensure the Safety of Subjects\***

The principal investigator will be primarily responsible for monitoring the safety of participants, and the safety and confidentiality of data. This will be done by following the best practices to ensure that we strictly adhere to the inclusion and exclusion criteria, and protections against risks outlines. The safety of each participant will be assessed on an individual basis throughout their involvement with the study. Any decline in function or participant responses that indicates a potential adverse effect will be reviewed individually and events will be reported to the IRB per UIC policy in a timely manner.

A member of the study personnel will be available to each participant throughout testing and will be monitoring participant safety. Participants will be instructed to immediately inform study personnel if any adverse effects of treatment are experienced. We will ask the participant to provide us with a phone number of a caregiver (or friend or family member) to contact in case of emergency. Any adverse events or unanticipated problems will be recorded and communicated to all study personnel as soon as possible. Study personnel will be trained to identify and manage adverse events or unanticipated problems involving risks to subjects or others. The PI will be notified immediately. Serious adverse events, study-related adverse events, and unanticipated problems will be reported within 24 hours to the UIC IRB. Participants will be removed from the study if the study procedures threaten the participants' safety or study procedures are unbearable. Any adverse events will be noted within the subject file.

In the event of injury related to this research, treatment will be available. However, the subject or his/her third party payer, if any, will be responsible for payment of this treatment. In the unlikely event that the subject requires emergency medical care during a study visit, 911 will be called

PROTOCOL TITLE: Effects of high-intensity inspiratory muscle training as a pre-cardiac rehabilitation intervention on cardiovascular functions in patients with heart disease

immediately. There is no compensation and/or payment for such medical treatment for such injury except as may be required by law.

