## **14.0 Withdrawal of Subjects\***

**14.1** Subjects will be withdrawn from the research without their consent according to the rules as follows; 1. Not attending more than 20% of supervised intervention sessions. 2. Not perform the measurements after the intervention (at the end of the 4th week). 3. Losing the product (Philips IMT) before the study ends. 4. Consent in writing that who wishes to end the study at any stage of the study.

**14.2** For patients meeting any of 14.1 (one of the above), the principal investigator will be notified. The principal investigator will notify that he/she has been terminated from the study by obtaining verbal consent from the relevant patient.

**14.3** Should the subject choose to withdraw, the health information already collected will continue to be used for research, however, no further health information will be collected. All health information and collected data will be stored coded on paper, electronically on UIC Health Data Box Folder. Only the PI and Co-Is will have access

PROTOCOL TITLE: Effects of high-intensity inspiratory muscle training as a pre-cardiac rehabilitation intervention on cardiovascular functions in patients with heart disease

to the key to the code that links coded data with the identity of the subject (which will be password protected).

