Title: High-intensity Inspiratory Muscle Training as a Pre-cardiac Rehabilitation in Heart Disease

NCT Number: NCT06127147

Date: 12/12/2023

Statistical Analysis Plan

Statistical analyses will be performed using SPSS version 21.0 (IBM, Armonk, NY). The Shapiro–Wilk test will be used to evaluate normality of the data distribution for each variable. The continuous variables will be reported as mean \pm SD, and the categorical variables will be presented in absolute frequencies and percentages. Nominal data will be compared using a Chi-square test. For comparison between the baseline and postintervention, the paired-samples t test or Mann–Whitney U test will be applied based on normality distribution. Change from the baseline values will also be calculated as the mean difference for each measure. Treatment effect and between-group comparisons will be evaluated based on mean differences using analysis of variance. Effect sizes will be provided as eta square, which are interpreted as small effect (0.01), medium effect (0.06), and large effect (0.14). The alpha value will be set at alpha = 0.05 for all outcomes.

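### No systematic adverse-event enquiry is specified, collection stops at voluntary withdrawal, and no summary by arm is planned, so harm data may be incomplete and open to differential ascertainment

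*Protocol*

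**What the plan says.** **Capture.** Protocol Section 18.0 names several routes by which an event can come to light:

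- A general commitment: "The safety of each participant will be assessed on an individual basis throughout their involvement with the study".
- Observation at assessments: "A member of the study personnel will be available to each participant throughout testing and will be monitoring participant safety".
- Staff review: "Any decline in function or participant responses that indicates a potential adverse effect will be reviewed individually".
- Self-report: "Participants will be instructed to immediately inform study personnel if any adverse effects of treatment are experienced".

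Staff are also to be trained to recognise events. Sections 5.1 and 11.2 put a physiotherapist on a video call for the training in both arms. Section 11.0 rules out collecting new information from medical records.

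**Recording.** "Any adverse events will be noted within the subject file". Events are also passed to all study staff and to the principal investigator. Serious events, study-related events and unanticipated problems go to the IRB within 24 hours. No adverse-event form, grading scale or dataset is named.

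**Exit.** When a subject chooses to withdraw, Section 14.3 provides that "the health information already collected will continue to be used for research, however, no further health information will be collected". Section 14.1 lists further grounds for withdrawal (too many missed sessions, no final measurements, a lost device). Section 18.0 adds removal where procedures endanger the participant or cannot be tolerated. No safety follow-up is described for any of these.

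**Analysis.** Neither Section 17.1 nor the SAP mentions adverse events. The SAP's plan for outcomes is framed around change in measurements: "Change from the baseline values will also be calculated as the mean difference for each measure".

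**The concern.** The instruction to participants is tied to cause. A patient must first decide that a symptom comes from the treatment and then report it. Section 15.4 names the likely complaints: "There is risk of dizziness, coughing, and/or feeling short of breath during the tests". People with heart disease may have these in either arm. A patient breathing against 60% of MIP may link them to the device more readily than one breathing through the same device with no load. The comparator is called a sham, but neither document says whether participants, physiotherapists or assessors are blinded.

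The patients who leave are the second worry. Someone who stops because of a symptom is among the most informative about harm. After a voluntary withdrawal, the outcome of that symptom and anything later in the planned four weeks goes uncollected, and the 24-hour reporting of serious events has no stated source of information for that person.

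What is at stake is the safety statement the trial can make. Section 1.0 describes the training as proven safe in related groups, and Revision 1 widened eligibility to patients with previous percutaneous intervention, heart failure or myocardial infarction. Without even enquiry and a table by arm, the trial could neither support nor qualify that description from its own data.

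**Working it through.** The documents give no adverse-event rate or safety precision figure, so there is nothing of the plan's own to reproduce. The check is mainly textual, with three short calculations for scale.

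**1. Which stated route covers which event?**

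- *During an assessment visit:* staff observation (Section 18.0). Covered.
- *During a training session:* the physiotherapist on video (Sections 5.1, 11.2). Observable, but no adverse-event question is specified.
- *Between sessions:* the only specific route is the participant's report of treatment effects (Section 18.0). The general promise of individual assessment states no method or schedule, and medical records are not a source (Section 11.0).
- *After voluntary withdrawal:* collection stops (Section 14.3).
- *After withdrawal on other grounds or removal for safety:* not described.

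The rule that any adverse event is recorded applies only to events that staff come to know about. The gap is therefore in events between sessions and after exit.

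**2. Opportunity to ask.** Sessions per participant: 2 a day × 5 days × 4 weeks = 40, the same in both arms. Across 44 participants: 44 × 40 = 1,760 planned supervised contacts. This is an upper figure, because up to 20% of sessions (0.20 × 40 = 8) can be missed before Section 14.1 applies. Three visits per participant come on top.

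**3. What differential reporting could do.** All rates here are assumed; none is in the documents. Recorded risk = true risk × proportion reported.

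- True risk 20% in both arms, 80% reported with load and 40% with sham: 0.20 × 0.80 = 16% against 0.20 × 0.40 = 8%, a ratio of 2.0 with no true difference. In 22 patients per arm that is 22 × 0.16 = 3.5 against 22 × 0.08 = 1.8 expected.
- 80% against 50%: ratio 0.80 / 0.50 = 1.6. For true risks of 10% to 30% the spurious difference is 0.10 × 0.30 = 3 points to 0.30 × 0.30 = 9 points.
- Equal reporting (80%/80% or 50%/50%): ratio 1.0, difference 0. Events are missed, but the arms are not distorted relative to each other.

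The ratio depends only on the relative reporting, on which the documents are silent.

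**4. Precision with complete capture.** If no events are seen in *n* patients, the one-sided 95% upper limit is 1 − 0.05^(1/*n*).

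- *n* = 22 (randomised per arm, Section 9.1): 1 − 0.05^(1/22) = 12.7%.
- *n* = 20 (the per-group number before the allowance for loss): 1 − 0.05^(1/20) = 13.9%.

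Each arm carries little information on harm, so a few unrecorded events matter, and a formal test between arms would say little.

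**The case against.** A reader who takes the self-report sentence alone might infer that events are captured only when a patient volunteers them, and that they go no further than the subject file. Section 18.0 does not support either inference. The same section provides individual assessment, staff observation, review of functional decline, trained staff, recording of any event, and routing to all personnel, the principal investigator and, where it qualifies, the IRB. This part of the defence stands.

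On withdrawal, the stop in Section 14.3 is written for subjects who choose to leave, and it keeps what was already collected. An event recorded before exit is not lost, and for other exits follow-up is undescribed rather than forbidden. That also stands, but the later course of an event and any new one remain uncovered.

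On bias, nothing in the documents shows how sham patients would attribute symptoms. They use the same device on the same schedule, and equal reporting gives no bias. It would be wrong to say that the harm data will be biased.

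On analysis, safety is not an endpoint in Section 4.0, and 22 per arm is weak for comparing harms however well events are collected. The general rules for categorical and nominal data could be stretched to cover events. These points argue against a formal test, not against even-handed collection and a descriptive table. The general rules do not name adverse events and commit nobody to reporting them by arm.

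**Conclusion.** The point holds as a gap in method. No systematic, attribution-neutral enquiry is specified. Between-session events rely on participants reporting what they take to be treatment effects. Collection ends at voluntary withdrawal, no safety follow-up is described for other exits, and no summary by arm is planned. Incompleteness is likely. Bias between arms is plausible because the load differs and no blinding is described, but it is not established. Its size could run from none (equal reporting) to a doubling of apparent risk (80% against 40%), and both of those are assumptions.

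The trial's efficacy analyses are not affected. The change is worth making because it is cheap and because, with 22 per arm, the harm data are thin to begin with.

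A related inconsistency should be reconciled at the same time. Sections 5.2 and 11.2 state that the device label leads to no expected adverse events, while Section 15.4, whose heading covers inspiratory muscle training, lists dizziness, coughing and breathlessness.

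**What to change.** - **Section 18.0:** ask one neutral question in both arms, in the same words, at fixed existing contacts: any new symptom, medical visit or hospital stay since last asked? Once a week at a supervised video session plus the 2-week and 4-week visits would be enough (4 + 2 = 6 times per participant, at most 6 × 44 = 264 in all). Asking at every session is possible but not needed. Record answers whatever the perceived cause, and enter them in the study dataset as well as the subject file.
- **Section 14.3:** ask any participant who stops or is removed for permission for one safety contact at the planned week 4, and for follow-up of any event still open. The consent wording must allow this.
- **SAP:** add a descriptive table by randomised arm of participants with any adverse event, participants with a serious adverse event, and exits with reasons. Do no formal testing, and give the upper limit where no events are seen.

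The cost is a few sentences in two protocol sections, one short table, a brief question at contacts already planned, and one phone call for each person who stops. The downside is that a few more minor events will be recorded and handled. Sample size, training and visit schedule do not change.

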## **19.0 Provisions to Protect the Privacy Interests of Subjects**

**Confidentiality and privacy:** A risk of this research is a loss of privacy or confidentiality. To minimize this risk and protect the participant's identity, we will store health information coded, using a subject ID # instead of the participant's name. Coding and locking of data will minimize the risk of confidentiality loss. All data collected during visits linking study and health information will also be coded and stored in the PI's laboratory, in addition to a UIC Health Box Data Folder. Only the PI and limited research personnel will have access to the key to the code that links coded data with the identity of the participant (which will be password protected) and this key will be stored in a UIC Health Box Data Folder.

## **20.0 Compensation for Research-Related Injury**

Compensation for research-related injury is not available.

## **21.0 Economic Burden to Subjects**

Participants will only be invited to the institution where the study will be conducted for measurement at the beginning, middle and end of the study. In total, each patient will have come 3 times. Participants will cover their own travel expenses. It is not foreseen that there will be any other expenses. This information will be stated in the consent form, and patients who volunteered to participate in this study must have accepted it.

## **22.0 Consent Process**

Informed consent will be obtained from the participant by the PI and/or research personnel according to UIC policy at the screening.

Proper informed consent will be given according to previous training in responsible conduct of research, protection of human research participants, and good clinical practice. Participants will be given a sufficient amount of time to review the consent document and ask any questions that they may have prior to providing their consent for participation.

- Informed consent and authorization will be obtained after eligibility screening has been confirmed, either during the routine patient visit at the outpatient Exercise Testing or Cardiac Rehabilitation Programs.

PROTOCOL TITLE: Effects of high-intensity inspiratory muscle training as a pre-cardiac rehabilitation intervention on cardiovascular functions in patients with heart disease

- Subjects expressing interest in participating in the study will communicate to key research personnel conducting the screening and consenting process. During the routine visit, oral consent will be obtained so that eligibility screening.
- An alteration of consent and a waiver of documentation of consent will be obtained for the eligibility screening.
- All investigators/study personnel carrying out recruitment will follow a detailed informed consent process that will include a careful review study requirements and explanation of the study protocol
- PI, and Key Research Personnel (research assistants) will obtain consent. Beside the PI and Co-Is, study staff thoroughly trained by the PI in the consenting process, and who have completed their CITI and HIPPA training may also obtain consent from subjects.
- The PI will keep the original signed consent form, and the subject will receive a copy.
- All consent documents and tracking sheets will be stored in [name] locked office in a locked filing cabinet.
- All data collected for the current research purposes will be stored coded.
- Subjects who do not speak English will be excluded (please see our inclusion and exclusion criteria for details). The process of recruitment, enrollment and obtaining written informed consent will only be in English. Lay language will be used to describe technical and medical terms

***\*Non-English Speaking Subjects***

- Subjects who do not speak English will not be enrolled (please see our inclusion and exclusion criteria for details).

***\*Request for Waiver or Alteration of Consent Process (If you will not obtain written consent, required information will not be disclosed, or the research involves deception)***

- Written consent will be obtain

***\*Subjects who are not yet adults (infants, children, teenagers)***

- NA

PROTOCOL TITLE: Effects of high-intensity inspiratory muscle training as a pre-cardiac rehabilitation intervention on cardiovascular functions in patients with heart disease

**\*Cognitively Impaired Adults**

- The Standardized Mini-Mental Test will be applied to the patients as in the heading 11.1.1 and anyone with a score below 24 will be excluded from the study.

**\*Adults Unable to Consent**

- Adults Unable to Consent will not be involved in study.

## **23.0 Process to Document Consent in Writing**

Informed consent will be obtained from the participant by the PI and/or research personnel according to UIC policy at the screening.

Proper informed consent will be given according to previous training in responsible conduct of research, protection of human research participants, and good clinical practice.

- Informed consent and authorization will be obtained after eligibility screening has been confirmed, either during the routine patient visit at the outpatient HF, Exercise Testing or Cardiac Rehabilitation Programs.
  - Subjects expressing interest in participating in the study will communicate to key research personnel conducting the screening and consenting process. During the routine visit, oral consent will be obtained so that eligibility screening.
  - An alteration of consent and a waiver of documentation of consent will be obtained for the eligibility screening.
- All investigators/study personnel carrying out recruitment will follow a detailed informed consent process that will include a careful review study requirements and explanation of the study protocol
- PI, and Key Research Personnel (research assistants) will obtain consent. Beside the PI and Co-Is, study staff thoroughly trained by the PI in the consenting process, and who have completed their CITI and HIPPA training may also obtain consent from subjects.
- The PI will keep the original signed consent form, and the subject will receive a copy.
- All consent documents and tracking sheets will be stored in [name] locked laboratory in a locked filing cabinet in Room 422 within the Applied Health Sciences Building.
- All data collected for the current research purposes will be stored coded.

**PROTOCOL TITLE: Effects of high-intensity inspiratory muscle training as a pre-cardiac rehabilitation intervention on cardiovascular functions in patients with heart disease**

- Subjects who do not speak English will be excluded (please see our inclusion and exclusion criteria for details). The process of recruitment, enrollment and obtaining written informed consent will only be in English. Lay language will be used to describe technical and medical terms

